8.3 Comparison Groups

Given the inherent difficulties in identifying an appropriate comparison group, several different methods may be used to review the data for any signals of teratogenicity. First, assuming a sufficient sample size is attained, the prevalence of birth defects in this Registry is compared to the prevalence observed in the MACDP, a population-based birth defects surveillance system that is administered by CDC (1998). The total prevalence of birth defects identified among births from 1968 through 2003 was 2.67% (Correa et al., 2007). However, the MACDP recognizes that prior to 1973 the annual prevalence was lower because of incomplete case ascertainment and that since 1973 the total defect prevalence has remained stable with only minimal year-to-year variation. The most recent five-year prevalence rate of 2.78% (6945 birth defect cases in 249,999 live births) from 1999 to 2003 is deemed the most appropriate comparator rate for this Registry (Correa et al., 2007). The baseline prevalence rate for specific birth defects varies.

The methods and patient population in this Registry differ from those used in the MACDP and therefore it may not be the most appropriate comparator. The primary objectives of MACDP are to monitor, regularly and systematically, births of malformed infants for changes in incidence or other unusual patterns suggesting environmental influences and develop a case registry for use in epidemiological studies. MACDP actively searches for birth defects among the 50,000 annual births to residents of metropolitan Atlanta's five counties and abstracts medical records at all Atlanta obstetric hospitals, Atlanta pediatric referral hospitals, genetics labs, and vital records (Correa-Villasenor et al., 2003). MACDP data has been used as a comparator group when examining birth defects for several existing pregnancy registries (acyclovir; sumatriptan; lamotrigine; and zidovudine) (Honein et al., 1999).

As a second method of analysis, the prevalence of birth defects among women in the Registry may be compared to the prevalence observed in published studies of pregnant women exposed to other drugs for similar indications if available at that time.

The Registry is committed to identifying other appropriate comparison groups and continues to research the literature and explore other sources to obtain appropriate background rates. It is important to note that other studies may vary in methodology, ascertainment and classification of birth defects, geographic location, and sample size, among other factors that could impact results. Therefore quantitative comparisons between the Registry and the studies reported in the literature may be difficult to interpret.

8.4 Sample Size

The Registry seeks to enroll approximately 350 prospective pregnancies. According to data from the general population, approximately 62% of clinically recognized pregnancies results in a live birth (FDA, 2002). Based on data from similar pregnancy registries, 10% are lost to follow-up. Therefore, the resulting number of live births is expected to be 196.

Compared to a baseline frequency of total birth defects of 2.78% from the MACDP (Correa et al., 2007), a sample size of 196 exposed live births provides 80% power to detect an overall prevalence rate of birth defects of at least 6.95%, which corresponds to a 2.5-fold increase over baseline. This estimate is based on the one-sample exact binomial method using a 2-sided type I error rate of 5%. Sample size considerations are based on the one-sample exact binomial test, although 95% confidence intervals (CI) will be used, rather than hypothesis testing, as the primary method to guide comparative assessments to the MACDP rate. For specific defects, the power to detect an increased risk varies depending on the frequency of the defect in the population and the evolving size of the exposed group.

8.5 Data Analysis

8.5.1 Birth Defects

For the primary analysis, the prevalence of birth defects reported to the Registry in the evaluable population is calculated by dividing the number of birth defects (i.e., the number of pregnancy outcomes occurring at or after 20 weeks gestation with a noted birth defect) by the total number of live births in the evaluable population. Pregnancy losses with reported birth defects occurring at or after 20 weeks gestation are included in the numerator of the estimate of risk for birth defects to increase sensitivity and to allow for comparison with the MACDP which calculates rates using this convention. A secondary analysis is conducted including pregnancy losses with reported birth defects occurring at any gestational age in the calculation of risk. An additional secondary analysis will be performed that only includes birth defects that are noted from ultrasound examinations (pre-natal or post-natal). Birth defects will be reported by outcome (live birth (overall and full-term or pre-term)), stillbirth, induced abortion (elective or therapeutic) and trimester of exposure. All defects detected <20 weeks of gestation will be described in the report. Additionally, birth defects noted by non-HCP reports will be reported descriptively.

Calculations of 95% confidence intervals (two-sided) for individual birth defect rates are based on the exact method using binomial probability distribution. The prevalence in exposed cases is compared with the observed prevalence in the MACDP (Correa et al., 2007). In addition, one-sample binomial tests at the two-sided 0.05 level are used to test the association of elevated levels of major birth defects in pregnancy exposures to Savella by comparing the observed proportion of birth defects in the Registry with rates from the MACDP.

Enrolled pregnancies that are LTFU without pregnancy outcome, as defined in section 6.2.6, will be enumerated in the interim/final report, but will not be included in the

calculation of risk. Prospectively enrolled pregnancies with an outcome will be included in the calculation of risk regardless of whether they are subsequently designated as infant LTFU.

If feasible, comparisons between the Registry and an appropriate external comparison group will be examined.

8.5.2 Demographic and Baseline Characteristics

Demographic and baseline characteristics are summarized for the evaluable population for birth defects. Demographics and baseline characteristics are also summarized for the LTFU population and compared to the evaluable population to assess potential differences. These data are reviewed for potential confounding factors that could affect interpretations of comparisons with the MACDP. Additional data including concomitant medications, maternal concurrent medical conditions, previous births with congenital anomalies, and Savella dosing information are summarized using simple descriptive statistics and data listings. Birth defect rates are also summarized by maternal age, gestational age at enrollment, earliest trimester of exposure, Savella dosing information, and concomitant medications. Further details are provided in the statistical analysis plan.

8.5.3 Adverse Pregnancy Outcomes

Overall and by-stratum point estimates of rates and 95% confidence intervals will be calculated for the following outcomes:

- Spontaneous abortions
- Stillbirths
- Induced abortions (overall and elective or therapeutic)
- Minor congenital anomalies,

Other adverse pregnancy outcomes among pregnancies exposed to Savella and their live births during the first year of life will be summarized as counts and percentages of the total number of prospective evaluable outcomes. Summaries will also be presented by subgroups including maternal age at conception (<25, 25-35, >35), family history of birth defects, smoking status, and alcohol use during pregnancy. Additional subgroups may be analyzed if deemed appropriate and necessary given the sample size. These other adverse pregnancy outcomes include:

- Functional deficits
- Alterations in fetal growth
- Transient or infectious conditions
- Biochemical abnormalities
- Pre-term infants with findings that persist and require surgical intervention

Strata are comprised by earliest trimester of exposure and potentially other variables as appropriate given the sample size, such as maternal age, history of birth defects, lifestyle variables, comorbidities, and concomitant drug exposures.

All chromosomal abnormalities, whether classified as a birth defect or other adverse outcome, will be displayed in a separate listing.

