5. GENERAL REGISTRY PROCEDURES

Enrollment may be initiated by pregnant patients or their HCPs. Patients are followed through their HCPs who are willing to provide information on maternal risk factors, pregnancy outcome, and infant health. Patient reports must be verified with an HCP. Section 5.3 describes this process in detail.

Enrollment should occur as early in pregnancy as possible, preferably before any prenatal testing has occurred; however, enrollment at any time during pregnancy is allowed. Near the estimated date of delivery, the Registry prompts the HCP to provide pregnancy outcome data. If a birth defect is reported, the Registry requests additional targeted follow-up information from the HCP. Follow-up of live-born infants continues through the first year of life.

Summary of Evaluations

	Maternal Contact		Maternal HCP Contact			Infant HCP Contact		Evaluator
Information Requested	Enrollment	Outcome	Registration	Interim Follow-Up (2 nd trimester)	Outcome Follow-Up	Follow-Up (at birth)	Follow-Up (4 and 12 months)	Targeted Follow-Up
Reporter Information and Permissions	_	-				-	-	-
Report source, permission to contact HCP (for pregnant patient), pediatrician, and alternate patient contact information as applicable (see section 5.3.1)	1	√ ^a	4					
Maternal Information								
Maternal characteristics (age, ethnicity, disease status)	1		✓					
Maternal prenatal information (LMP, EDD, CEDD, prenatal test results & timing)	1		1	√ ^a	√ ^a			
Obstetrical history, family history (maternal and paternal)	✓		1					✓ ^d
Savella therapy (dosage, routes, start/stop dates)	1		1	√ ^a	√ ^a			
Concomitant medications (Rx, OTC, dietary supplements, herbals), during pregnancy (dosage, routes, start/stop date of administration), and alcohol, tobacco, and recreational drug use during pregnancy	4		~	√ ^a	√ ^a			√ ^d
Maternal concurrent medical conditions, pregnancy complications, maternal adverse events	1		1	√ ^a	√ ^a			
Outcome of Pregnancy Information								
Pregnancy Status	✓	✓	✓	✓	√ ^a			
Outcome data (fetal loss, live birth, gestational age, weight)		✓		✓ ^b	✓	✓		
Birth defect noted, description, attribution, if applicable				✓ ^b	✓			
Other factors that may have contributed to outcome (etiology)				✓ ^b	✓			✓ ^d
Infant Follow-up Information								
Infant assessments: anthropometric, developmental, functional, growth, postnatal conditions, medications,						✓ ^b	1	
Birth defect noted, description, attribution, if applicable						√ ^b	1	

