6.2.3 Evaluable Registry Reports

An evaluable report is a case, submitted or verified by a HCP, containing at least the minimum criteria for Registry enrollment, and is not lost to follow-up. Prospectively reported evaluable cases with known outcomes are included in the primary analyses for the Interim Report produced annually and the Final Report. Retrospective reports are summarized separately in the Interim Reports and the Final Report.

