8.2 Analysis Parameters for Birth Defects

Pregnancy outcomes are categorized as live birth (full-term or pre-term), stillbirth, spontaneous abortion, induced abortion (elective or therapeutic), ectopic pregnancy, and molar pregnancy. Most structural defects have their origins in the first trimester of pregnancy; the period of organogenesis. Therefore, the outcome data (i.e., birth defects and other pregnancy outcomes) may be stratified by the earliest trimester of exposure to Savella (first trimester, second trimester, and third trimester).

Gestational weeks are calculated beginning from the first day of the LMP when it is considered to be a reliable predictor of the EDD. However, if a CEDD is available (e. g., by ultrasound), the CEDD is preferred for calculating gestational weeks. The second

trimester begins at 14 weeks and 0 days, and the third trimester begins at 28 weeks and 0 days.

Descriptive statistics are the primary approach for summarizing data from this pregnancy registry. Confidence intervals are provided for purposes of estimation and are not used for statistical inference.

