- Pregnancy Category B No evidence of risk in humans: Adequate, well-controlled studies in pregnant women have not shown increased risk of fetal abnormalities despite adverse findings in animals, or, in the absence of adequate human studies, animal studies show no fetal risk. The chance of fetal harm is remote, but remains a possibility.
- **Pregnancy Category C** Risk cannot be ruled out: Adequate, well-controlled human studies are lacking, and animal studies have shown a risk to the fetus or are lacking as well. There is a chance of fetal harm if the drug is administered during pregnancy, but the potential benefits may outweigh the potential risk.
- Pregnancy Category D Positive evidence of risk: Investigational or post-marketing data show risk to the fetus. Nevertheless, potential benefits may outweigh the potential risk.

- **Pregnancy Category X** Contraindicated in pregnancy: Studies in animals or humans, or investigational or post-marketing reports, have shown fetal risk which clearly outweighs any possible benefit to the patient.
- **Premature Birth** An infant at outcome < 37 weeks gestational age or if gestational age not available, weighing < 2,500 grams as defined by CDC's criteria in the MACDP manual.
- **Prospective report** Any report of a pregnancy exposure to the Registry drug reported before the outcome of pregnancy is known.
- **Retrospective report** Any report of a pregnancy exposure to the Registry drug reported after the outcome has occurred or for which an abnormal condition was identified on a prenatal test.
- Spontaneous Abortion Fetal death or expulsion of products of conception prior to 20 weeks gestation or if the gestational age is unknown, a fetus weighing less than 350 grams. Terminology may include: missed abortion, blighted ovum, incomplete abortion, and inevitable abortion
- **Stillbirth** A fetal death occurring at 20 weeks gestation or greater, or if the gestational age is unknown, a fetus weighing greater than or equal to 350 grams.
- **Temporality Assessment** The determination of the probable association or nonassociation of the timing of the maternal exposure in pregnancy relative to the probable timing of organogenesis of a defect.
- Term Birth An infant at outcome ≥ 37 weeks gestational age or if gestational age is not available, weighing ≥ 2,500 grams as defined by CDC's criteria in the MACDP manual.

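### Spontaneous abortion rates ignore gestational age at enrollment: the third-trimester-exposure cell is zero by construction, and a crude overall rate is biased low

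*Protocol*

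**What the plan says.** All places are in the Protocol.

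- **Entry.** Section 5 prefers early enrollment, but "enrollment at any time during pregnancy is allowed". Under Section 6.2.1 a prospective report follows exposure.
- **Losses before first contact.** Under Section 6.2.2, a report made after the outcome is accepted only if a birth defect was noted, and even then it is kept out of the statistical analysis.
- **Outcome.** The Glossary defines spontaneous abortion as "Fetal death or expulsion of products of conception prior to 20 weeks gestation".
- **Estimate.** Sections 1 and 2 make its prevalence a secondary objective. Section 8.5.3 promises: "Overall and by-stratum point estimates of rates and 95% confidence intervals will be calculated for the following outcomes". Spontaneous abortion is the first outcome listed.
- **Strata.** Section 8.5.3 continues: "Strata are comprised by earliest trimester of exposure and potentially other variables as appropriate given the sample size". The Synopsis says the same. Under Section 8.2 the second trimester starts at 14w0d, and "the third trimester begins at 28 weeks and 0 days".
- **Denominator.** None is named for spontaneous abortion. The only one in Section 8.5.3 belongs to the other adverse outcomes, which are "summarized as counts and percentages of the total number of prospective evaluable outcomes".
- **Time at risk.** Delayed entry and left truncation are not mentioned. Section 8.5.2 uses gestational age at enrollment only to summarize birth defect rates, and the biases listed in Section 8.6 do not include time of entry.

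**The concern.** A woman who enrolls at week 14 has already passed through most of the weeks in which she could have had a spontaneous abortion. One who enrolls at week 20 or later cannot have one at all. If both count fully in the denominator, the rate describes when women enrolled as much as it describes loss.

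The split by first exposure adds a second form of the same problem. To be first exposed in a later trimester, a pregnancy must have survived to it. The table would show loss falling from first- to second- to third-trimester exposure even if the drug had no effect.

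At stake is a falsely reassuring figure. The Background section records that the FDA asked for pregnancy and fetal outcomes to be compared with an unexposed population. A reader who sets the registry's crude rate beside a rate counted from early pregnancy could miss a real increase.

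**Working it through.** **1. The plan's own figures.** The Protocol states no expected rate of spontaneous abortion, so there is none to reproduce. Its sample-size figures reproduce: 350 × 0.62 × 0.90 = 195.3 live births (stated 196). The exact binomial test with n = 196 and 2.78% against 6.95% rejects at 11 or more cases, with upper-tail error 0.022 and power 0.807 (stated 80%). These figures concern birth defects and are not affected.

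**2. What follows from the definitions alone.** The event must occur before 20w0d.

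| First exposure | Weeks in which a spontaneous abortion can follow exposure |
|---|---|
| Before 14w0d | from exposure to week 19 |
| 14w0d to 27w6d | weeks 14–19 at most; none if first exposed at 20w0d or later |
| 28w0d or later | none |

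The last cell is 0/n. Its exact 95% upper limit is 1 − 0.025^(1/n): 30.8% for n = 10, 16.8% for n = 20 and 7.1% for n = 50. It reflects only the number of women. In every cell, enrollment after exposure shortens the observed window further.

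**3. Size of the bias in a crude proportion (illustration).** Every input here is an assumption. The true loss over weeks 5–19 is R. The weekly hazard is h_w = −ln(1 − R) × g^(w−5) / Σ g^(k−5), summed over k = 5 to 19. Here g = 1 is flat, and g = 0.85 or 0.75 falls by 15% or 25% per week. The risk still observable after entry at week e is 1 − exp(−Σ h_w) over w = e to 19, and zero from week 20.

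Example with R = 15% and g = 0.85: −ln(0.85) = 0.1625. Weeks 14–19 carry 0.158 of the total hazard, so the risk after entry at week 14 is 1 − exp(−0.1625 × 0.158) = 2.5%. Entry at week 8, 10 or 12 leaves 9.0%, 6.2% or 4.1%. Averaging over uniform entry weeks gives the crude rate:

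| Entry weeks | R = 15%, g = 0.85 | R = 15%, g from 0.75 to 1 | R from 10% to 20%, g from 0.75 to 1 |
|---|---|---|---|
| 5–12 | 8.8% | 6.8%–11.7% | 4.5%–15.7% |
| 6–20 | 4.4% | 2.9%–7.2% | 1.9%–9.7% |
| 6–36 | 2.1% | 1.4%–3.5% | 0.9%–4.7% |

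For R = 15%, the risk of loss after reaching 14 weeks is 1.0% to 6.3% across these hazard shapes. That is the most the second-trimester cell could show.

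**4. Does delayed entry repair it?** In a simulation with R = 15%, g = 0.85 and entry uniform over weeks 5–36, the crude proportion was 2.5% and the product-limit estimate with delayed entry was 14.9%. When the first entry was at week 6, delayed entry gave about 13%, because week 5 was never observed.

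**5. Pre-term birth, for contrast.** Assume 10% pre-term: 0.7% in weeks 20–27, 0.9% in weeks 28–31, 1.2% in weeks 32–33 and 7.2% in weeks 34–36. The risk after entry at week 28 is (0.9 + 1.2 + 7.2) / (100 − 0.7) = 9.4%. It is 8.5% at week 32, 7.4% at week 34 and zero from week 37.

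**The case against.** **The estimator may be in the SAP.** The Protocol does not call the spontaneous abortion rate a simple proportion, Section 8.5.2 defers details to an SAP that is not at hand, and the denominator in Section 8.5.3 governs only the other outcomes. This stands as far as it goes: the downward bias of the overall rate is conditional on a crude proportion. It does not remove the point, because the Protocol itself sets the trimester strata and the zero cell follows from them under any estimator.

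**The outcome is descriptive.** Section 2 calls the Registry primarily exploratory, and Section 8.2 says confidence intervals are for estimation, not inference. No test or decision rule uses spontaneous abortion. This stands and limits the weight of the point.

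**Stronger readings that the documents do not support.**

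- A reader might extend the point equally to pre-term birth. It is a secondary objective but is not in the Section 8.5.3 list of rates, and Section 8.2 makes its trimester split optional. No trimester cell is zero, since the third trimester contains weeks 28–36. Late entry can still lower a crude pre-term rate, but by less under the assumptions above.
- A reader might conclude that the overall rate must fall below any background figure. The Protocol gives no background figure for spontaneous abortion; the comparator in Section 8.3 is for birth defects.
- A reader might add an upward bias in interim reports, since early losses resolve before ongoing pregnancies deliver. Section 6.2.3 does limit analyses to known outcomes, but each report is cumulative and replaces the last (Section 13.1), so this effect is transient.

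**Delayed entry is not a complete cure.** It cannot recover weeks before the earliest enrollment, and it assumes that time of enrollment is unrelated to the risk of loss. Section 8.6 concedes that voluntary reporting may be selective. This stands and should be stated.

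**Conclusion.** The point holds for spontaneous abortion. Two parts rest on the Protocol's definitions alone: the third-trimester-exposure cell is zero by construction, and the second-trimester cell is conditional on survival to 14 weeks. A third part, the downward bias of the overall rate, holds if the rate is a proportion over all prospective evaluable pregnancies and women enroll after risk has begun. Its direction is then certain, but its size depends on an enrollment pattern, hazard shape and true loss that the documents do not give.

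This is worth correcting before the rates are reported, but it is not a flaw in the Registry's main result.

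**What to change.** **Section 8.5.3**

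- Estimate spontaneous abortion as cumulative incidence to 20w0d on the gestational-age scale, with delayed entry at enrollment, in pregnancies enrolled and exposed before 20w0d. Treat induced abortion as a competing event. Because enrollment follows exposure, entry at enrollment deals with both late enrollment and late first exposure.
- Drop the third-trimester cell for spontaneous abortion. Show a second-trimester cell only as risk conditional on reaching 14 weeks.
- Base stillbirth on pregnancies under observation at or after 20 weeks.
- Limit any pre-term estimate to pregnancies enrolled before 37w0d.

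**Section 8.6**

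- Add left truncation to the listed biases. State that weeks before the earliest enrollment cannot be recovered, and that the method assumes enrollment time is unrelated to risk of loss.

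**Cost.** A change of wording and standard survival code. The report date, LMP or corrected due date, and gestational age at outcome are already collected (Sections 4.2, 5.3.1 and 5.5.2). The price is small risk sets in the early weeks and wider intervals.

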2. PURPOSE AND RATIONALE

The purpose of Allergan's Savella Pregnancy Registry (Registry) is to monitor pregnancies exposed to Savella (milnacipran HCl) to determine the risk of birth defects. Because Savella is commonly used among reproductive age women, this pregnancy registry has been established to prospectively assess the birth outcomes of babies born to women that are exposed to Savella during pregnancy. The lack of human fetal safety data concerning this product makes such a monitoring system an important component of epidemiologic research on the safety of Savella. Due to the lack of human data regarding fetal safety, the Registry is primarily exploratory.

The primary objective of the Savella Pregnancy Registry is:

• To estimate the prevalence of major congenital anomalies among offspring of women exposed to Savella during pregnancy.

The secondary objectives are

- To estimate the prevalence of full-term live births (≥37 weeks), pre-term live births (<37 weeks), recognized spontaneous abortions, stillbirths, induced abortions (elective and therapeutic), chromosomal abnormalities, and minor congenital anomalies
- 2) To summarize
- Serious pregnancy complications and maternal adverse events
- Adverse pregnancy outcomes
- Serious adverse outcomes observed during the first year of life in infants born from exposed pregnancies, including alterations in fetal/infant growth, presence of functional deficits, biochemical abnormalities, transient or infectious conditions, symptoms of poor neonatal adaptation (i.e., neonatal withdrawal), and persistent pulmonary hypertension of the newborn

3. **REGISTRY DESIGN**

This is a prospective, observational, exposure-registration and follow-up registry of women exposed to Savella during pregnancy. The Registry is strictly observational; the schedule of patient visits and treatment regimens are at the discretion of the treating physician. HCPs submit patient data that are routinely collected and documented in the patient's medical record.

4. **REGISTRY POPULATION**

The Registry population includes women with any Savella exposure during pregnancy, defined as exposure on or after the first day of the LMP. Women must be \geq 18 years of age and reside in the US.

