5.6.2 Information Collected at Pediatric Follow-up

Infant at outcome

- Date of follow-up evaluation
- Current age of infant (at the time of assessment)
- Gender
- Gestational age at birth
- APGAR scores at birth
- Birth weight, length, head circumference and corresponding population-based percentiles
- Birth defect(s) and details, if noted
 - Type of birth defect(s)
 - Attribution to Savella drug therapy
 - Other factors that might have contributed to the outcome
 - Defect absent/present on pre- or post-natal test
- Chromosomal abnormalities and details, if noted
- Immediate post-natal health problems requiring resuscitation, admission to the neonatal intensive care unit (NICU)
- Medications
- Surgical interventions required of pre-term infants
- Other serious infant adverse outcomes noted on physical examination
 - Evidence of alterations in fetal/infant growth (e.g., intrauterine growth restricted, small for gestational age, etc.)
 - Presence of functional deficit (e.g., poor muscle tone, abnormal reflexes)
 - Presence of biochemical abnormality
 - Presence of transient or infectious conditions
 - Symptoms of poor neonatal adaptation (i.e., neonatal withdrawal)
 - Persistent pulmonary hypertension of the newborn

Infant at 4 and 12 months

- Date of follow-up evaluation
- Current age of infant (at the time of assessment)
- Birth weight, length, head circumference and corresponding population-based percentiles
- Birth defect(s) detected since last assessment and details, if noted
 - Type of birth defect(s)
 - Attribution to Savella drug therapy
 - Other factors that might have contributed to the outcome
 - Defect absent/present on pre- or post-natal test
- Chromosomal abnormalities and details, if noted
- Medications
 - Other serious infant adverse outcomes noted on physical examination

- Evidence of alterations in infant growth
- Presence of functional deficits
- Developmental delays

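### Section 8.5.3 expresses first-year infant outcomes as percentages of all evaluable outcomes, fetal losses included, which understates them and does so unevenly by trimester of exposure

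*Protocol*

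**What the plan says.** Section 8.5.3 introduces a set of "Other adverse pregnancy outcomes among pregnancies exposed to Savella and their live births during the first year of life", which "will be summarized as counts and percentages of the total number of prospective evaluable outcomes". The set has five items: functional deficits, alterations in fetal growth, transient or infectious conditions, biochemical abnormalities, and pre-term infants whose findings persist and need surgery.

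An evaluable report under Section 6.2.3 is one submitted or verified by a healthcare provider, "containing at least the minimum criteria for Registry enrollment, and is not lost to follow-up". Nothing there limits it to live births. Section 8.2 is explicit about what an outcome is: "Pregnancy outcomes are categorized as live birth (full-term or pre-term), stillbirth, spontaneous abortion, induced abortion (elective or therapeutic), ectopic pregnancy, and molar pregnancy". By contrast, Section 8.5.1 divides birth defects by live births.

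The synopsis promises overall and by-stratum estimates with 95% confidence intervals for these same infant outcomes, with earliest trimester of exposure as the named stratum.

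On loss to follow-up, Section 6.2.7 defines a pregnancy loss and an infant loss separately and keeps both out of the statistical analyses. Section 8.5.1 makes an exception for infants lost later, but only for the birth-defect risk.

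On collection, the objective in Section 2 covers "Serious adverse outcomes observed during the first year of life in infants born from exposed pregnancies" and names biochemical abnormalities and transient or infectious conditions. Section 5.6.2 itemizes both of these, and surgery in pre-term infants, at the birth assessment. Under other serious outcomes the 4- and 12-month list names only infant growth, functional deficits and developmental delays. It also repeats the birth item "Birth weight, length, head circumference and corresponding population-based percentiles".

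**The concern.** Apart from alterations in fetal growth, every item in this set can be seen only in a live-born infant. A fetal loss can never enter the numerator, yet it counts in the denominator. The resulting percentage is not a risk in any population at risk, and the error runs toward apparent safety. The denominator is stated in the protocol itself, so an analysis plan that used live births would depart from it.

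The dilution also depends on how many losses a group contains. Any comparison between groups with different live-birth shares mixes infant risk with loss frequency. Earliest trimester of exposure is the most exposed comparison, because early losses fall almost by construction in the early-exposure group.

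The collection question is separate. Where an outcome is to be summarized over the first year but is not itemized after birth, later events depend on a general question or on the clinician's choice to report.

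**Working it through.** **Inputs (Section 8.4).** Enrollment: "The Registry seeks to enroll approximately 350 prospective pregnancies". Live-birth share: "approximately 62% of clinically recognized pregnancies results in a live birth". Pregnancy loss to follow-up: 10%. Multiple births are ignored.

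**1. The plan's own figure.** Live births = 350 × 0.62 × (1 − 0.10) = 195.3. The protocol states 196, so the figure reproduces to within rounding.

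**2. The Section 8.5.3 denominator on the same inputs.** Evaluable outcomes = 350 × (1 − 0.10) = 315. Outcomes that are not live births = 315 − 195.3 = 119.7, or 119.7/315 = 38%.

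**3. Size of the dilution.** For e infant events, the plan reports e/315; per live birth the figure is e/195.3. The ratio is 195.3/315 = 0.62 whatever e is. With e = 10: 10/315 = 3.2% against 10/195.3 = 5.1%.

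**4. Range for the live-birth share.** The 62% is a general-population planning figure. The other shares below are assumptions; 315 evaluable outcomes and 10 events are held fixed.

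| Live-birth share | Live births | As written (10/315) | Per live birth | Factor |
|---|---|---|---|---|
| 0.62 (protocol) | 195.3 | 3.2% | 5.1% | 0.62 |
| 0.70 | 220.5 | 3.2% | 4.5% | 0.70 |
| 0.80 | 252.0 | 3.2% | 4.0% | 0.80 |
| 0.90 | 283.5 | 3.2% | 3.5% | 0.90 |

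**5. Strata by trimester of first exposure.** In a stratum with live-birth share s and infant risk r per live birth, the reported percentage is r × s. The glossary places spontaneous abortion before 20 weeks, and Section 8.2 starts the third trimester at 28 weeks. A pregnancy first exposed in the third trimester therefore cannot end in spontaneous abortion, whereas one first exposed in the first trimester can. As an illustration with assumed shares and the same r = 5.1% in both strata: s = 0.62 gives 5.1% × 0.62 = 3.2%; s = 0.90 gives 5.1% × 0.90 = 4.6%. The whole gap comes from the denominator.

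**6. Collection, side by side.**

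| Item | Section 5.6.2, birth | Section 5.6.2, 4 and 12 months | Elsewhere |
|---|---|---|---|
| Functional deficits | listed | listed | ticked in Summary of Evaluations |
| Growth | listed | listed; weight item says birth weight | anthropometric and growth ticked |
| Biochemical abnormalities | listed | not itemized | Section 7.1.2: if the clinician thinks it important |
| Transient or infectious conditions | listed | not itemized | Section 7.1.2, same condition |
| Surgery in pre-term infants | listed | not itemized | no specific entry; at most under general postnatal conditions |

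The general row for postnatal conditions is ticked at 4 and 12 months in the Summary of Evaluations, so these parts of the protocol differ in how specific they are.

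**The case against.** The strongest reply is that little turns on this. The Registry calls itself primarily exploratory, the infant outcomes fall under the objective to summarize rather than to estimate prevalence, and descriptive statistics are the main approach. Counts are reported beside percentages and live births are reported as well, so a reader can recompute the overall rate. No event is lost through the denominator. All of this stands, and it limits the severity. It does not make the printed percentage right.

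It is also fair that 62% may be too low. Enrollment is allowed at any time in pregnancy, and a woman who enrolls late has already passed the period of early loss. The factor could be nearer 0.80 or 0.90 than 0.62. For the same reason the size of the trimester distortion depends on when women enroll.

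Three stronger readings are tempting, and the documents do not support them:

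- **Infants without pediatric follow-up are also in the denominator.** With an assumed 20% infant loss the factor would be 195.3 × 0.80/315 = 0.50. But Section 6.2.7 keeps infant losses out of the statistical analyses, the exception in Section 8.5.1 concerns birth defects only, and the protocol gives no infant loss rate. At most the text is ambiguous.
- **The pre-term surgery item is understated more than tenfold.** If 12% of live births were pre-term (about 23 infants) and 4 needed surgery, both assumed, 4/315 = 1.3% could be set against 4/23 = 17%. Most of that gap comes from conditioning on pre-term birth. Per live birth the figure is 4/195 = 2.1%, and counting the item per live birth is legitimate.
- **Postnatal growth cannot be assessed and later events are not asked for.** The Summary of Evaluations ticks anthropometric, growth and postnatal conditions at 4 and 12 months, the later list includes alterations in infant growth, and Section 7.1.2 allows discretionary reporting. What remains is an inconsistency, not a demonstrated absence of data.

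Alterations in fetal growth can also be recorded when a pregnancy ends in loss (Section 5.4.2), so the wider denominator is defensible for that item.

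**Conclusion.** The denominator in Section 8.5.3 is wrong for the four infant-only outcomes. On the protocol's own planning inputs, and before any infant loss to follow-up, it reports about 0.62 of the rate per live birth, a relative understatement of 38%. At an assumed live-birth share of 80% the understatement is 20%. It falls more heavily on first-trimester exposure, provided some women in that stratum enroll early enough for a spontaneous abortion to be observed and other losses do not offset it.

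The collection point holds only as a need to reconcile Section 5.6.2 with the Summary of Evaluations and Section 7.1.2. It is not shown to bias the percentages by a known amount.

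The outcomes concerned are secondary and descriptive, and the primary birth-defect prevalence already uses live births. The correction is worth making, but the Registry's main result does not depend on it.

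**What to change.** **Section 8.5.3.** For functional deficits, transient or infectious conditions, biochemical abnormalities and the pre-term surgery item, use live-born infants with pediatric follow-up information as the denominator, consistent with Section 6.2.7. Show the number of infants lost to follow-up beside each percentage. Keep all prospective evaluable outcomes for pregnancy-level events and, if wanted, for alterations in fetal growth. The pre-term surgery item may also be shown per pre-term live birth. Apply the same denominators within strata and subgroups.

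**Section 5.6.2.** Reconcile the 4- and 12-month list with the Summary of Evaluations and Section 7.1.2. Replace birth weight by current weight if that is what is meant. Either itemize biochemical abnormalities, transient or infectious conditions and surgery in pre-term infants at those visits, or state that they are summarized only as far as the birth assessment and discretionary reports allow.

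**Cost.** About a sentence or two in Section 8.5.3, with no new data needed for the denominator, and a small revision of one list and its form covering information the pediatrician would ordinarily have in the chart.
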